5.3 Safety Outcome Measures

- Adverse events (AEs): Including peritonitis, gastrointestinal reactions (e.g., abdominal distension, diarrhea), metabolic acidosis, etc.; recorded throughout the study period.
- Serious adverse events (SAEs): Including death, life-threatening events, prolonged hospitalization, permanent disability, etc.; reported to the Ethics Committee and sponsor within 24 hours of identification.

6. Study Procedures

6.1 Timeline

Phase	Duration	Key Activities
Preparation & Rolling Recruitment	January 2026 – June 2027 (18 months)	Screen participants, verify eligibility, obtain informed consent, complete baseline assessments (recruitment continues until 6 months before study end to ensure all participants finish 6-month follow-up)
Intervention & Follow-up (Per Participant)	6 Months Post-Enrollment	Implement intervention, conduct biweekly follow-up (record UF and AEs), perform 3-month serum albumin testing
Final Post-Intervention & Study Closure	July 2027 – December 31, 2027 (6 months)	Complete 6-month outcome assessments for the last enrolled participants; finalize data verification, statistical analysis, and study report writing

6.2 Specific Procedures

- Baseline Assessment (Enrollment Day):** Collect demographic data, perform physical examination, conduct laboratory tests (blood, urine, dialysate samples), evaluate peritoneal function, complete SGA scoring, and measure muscle mass.
- Intervention Period:** Conduct biweekly follow-up to record UF volume, AEs and assess medication compliance. Perform serum Alb testing and AE review at the 3-month follow-up.
- 6-Month Post-Intervention:** Repeat all baseline assessments to measure outcome indicators.
- Withdrawal Visit:** Complete safety assessments and data supplementation for participants who withdraw from the study.

7. Statistical Analysis Plan

7.1 Statistical Software

SPSS 26.0

7.2 Data Analysis Principles

- **Intention-to-Treat (ITT) Analysis:** All enrolled participants will be included in the ITT set, regardless of protocol adherence.
- **Per-Protocol (PP) Analysis:** Participants who complete the full intervention and have no major protocol violations will be included in the PP set for sensitivity analysis.

7.3 Descriptive Statistics

- Continuous data: Presented as mean \pm standard deviation (SD) if normally distributed, or median (interquartile range [IQR]) if non-normally distributed.
- Categorical data: Presented as counts (percentages).

7.4 Inferential Statistics

- **Primary Outcome:** Compare serum Alb levels before and after intervention using paired t-tests (if normally distributed) or Wilcoxon signed-rank tests (if non-normally distributed).
- **Secondary Outcomes:** Use the same statistical methods as the primary outcome for continuous indicators; use Chi-square tests or Fisher's exact tests for categorical safety indicators.
- **Correlation Analysis:** Use Pearson or Spearman correlation tests to explore associations between nutritional indicators and other outcomes.
- **Significance Level:** Two-tailed $\alpha = 0.05$.

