5.1 Primary Outcome Measure

Serum albumin (Alb) level: Measured at baseline (enrollment day), 3 months, and 6 months post-intervention.

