7.5 Sample Size Justification

Based on a pre-study pilot ($n=20$), the standard deviation (σ_d) of serum Alb changes is 4 g/L, and the clinically meaningful difference (δ) is 3 g/L. With a two-tailed $\alpha=0.05$ and power=80%, the minimum sample size is 14. Accounting for a 15% withdrawal rate, 50 participants are enrolled to ensure result robustness.

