7.6 Missing Data Handling

Missing data will be addressed using multiple imputation methods to minimize bias in the analysis results.

8. Data Management & Quality Control

- **Data Collection:** Use Electronic Case Report Forms (eCRFs) combined with paper records; anonymize data using unique study IDs to protect participant privacy.
- **Data Verification:** Implement double data entry, with all modifications tracked and documented in the audit trail.
- **Equipment Calibration:** Calibrate testing instruments every 3 months to ensure measurement accuracy.
- **Personnel Training:** Provide uniform training on study protocols and Standard Operating Procedures (SOPs) to all study personnel before study initiation.
- **Metadata Removal:** Redact and remove metadata from all electronic documents before submission to ensure compliance with data privacy regulations.

9. Ethics & Compliance

- The study complies with the 2024 Declaration of Helsinki, Good Clinical Practice (GCP), and relevant national regulations.
- Approved by the Ethics Committee of Shanghai Tenth People's Hospital (Approval No.: SHSY-IEC-6.0/26K8/P01; Approval Date: January 9, 2026).
- Informed consent will be obtained from all participants (or legal representatives) before enrollment.
- All personally identifiable information (PII) and confidential commercial information will be redacted before any public disclosure.

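### The primary test is chosen by a normality check, and on the Wilcoxon branch it no longer tests the mean change on which the trial is sized

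*Protocol*

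**What the plan says.** Protocol section 5.1 defines the primary outcome: "Serum albumin (Alb) level: Measured at baseline (enrollment day), 3 months, and 6 months post-intervention". Section 7.4 compares albumin before and after the intervention "using paired t-tests (if normally distributed") or by "Wilcoxon signed-rank tests (if non-normally distributed"), at two-sided 0.05. It names no normality check and no threshold, and does not say whether the albumin levels or the within-patient changes are examined.

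Section 7.5 sizes the trial on the mean of the changes: "the standard deviation (σ_d) of serum Alb changes is 4 g/L" and "the clinically meaningful difference (δ) is 3 g/L". Section 7.2 puts all enrolled participants in the ITT set. Section 7.6 adds: "Missing data will be addressed using multiple imputation methods". It gives no pooling rule.

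**The concern.** The protocol fixes a rule under which the trial's own data select the primary test, and the two candidates have different null hypotheses. The paired t-test asks whether the mean change is zero, which is the quantity used in section 7.5. The signed-rank test asks whether the changes are symmetric about zero, in effect whether their pseudo-median is zero. These agree when changes are symmetric and separate when they are skewed, and skewed data often trigger the switch. A significant result on that branch could then be read as evidence about the 3 g/L mean change when it is not.

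There is a smaller practical matter. Rubin's rules combine an estimate and its standard error from each imputed data set. The signed-rank test gives a rank statistic and a p-value, so that branch does not fit the usual pooling for section 7.6.

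**Working it through.** **Inputs from the protocol.** SD of change 4 g/L, difference 3 g/L, two-sided alpha 0.05, power 80%, minimum n = 14, 50 enrolled, 15% withdrawal (all 7.4 and 7.5). Completers: 50 × 0.85 = 42.5, so about 42. The imputed ITT set has 50.

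**Inputs assumed, because the protocol does not give them.** The normality check is Shapiro-Wilk at 0.05 on the changes. Skewness runs from 0 to 2.0 (gamma distributions), with a lognormal as an extreme and a t distribution with 3 df for symmetric heavy tails.

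**Step 1: the plan's own figure.** n = (SD × (z0.975 + z0.80) / difference)² = (4 × (1.960 + 0.842) / 3)² = 13.95, rounded up to 14. This reproduces, and confirms that the sizing is for a mean change. (With the t distribution, 14 gives 73.7% power and 16 gives 80.1%; with 50 enrolled this has no consequence.)

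**Step 2: the two nulls differ under skewness.** For a gamma distribution with shape k, shifted to mean 0 and scaled to SD 4, the median is 4 × (gamma median − k) / √k. For k = 1 (skewness 2.0) this is 4 × (0.693 − 1) = −1.23 g/L. For k = 4 (skewness 1.0) it is −0.66 g/L. The mean change is exactly zero, yet the centre that a rank test responds to is not.

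**Step 3: rejection rate when the true mean change is zero.** There were 10,000 simulated trials per row. The Monte Carlo standard error at 5% is √(0.05 × 0.95 / 10,000) = 0.2 percentage points.

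| Changes | n = 42: switched to Wilcoxon | n = 42: t-test / rule | n = 50: switched to Wilcoxon | n = 50: t-test / rule |
|---|---|---|---|---|
| Normal | 5% | 4.9% / 4.9% | 5% | 4.8% / 4.9% |
| Skewness 0.5 | 19% | 5.3% / 6.0% | 23% | 4.9% / 5.6% |
| Skewness 1.0 | 60% | 5.4% / 8.3% | 69% | 5.6% / 9.4% |
| Skewness 1.4 | 90% | 5.9% / 12.3% | 95% | 5.6% / 13.4% |
| Skewness 2.0 | 99.8% | 6.6% / 19.5% | 100% | 6.8% / 22.7% |
| Lognormal | 99% | 8.2% / 28.8% | 99.9% | 7.6% / 33.2% |
| Symmetric, t with 3 df | 58% | 4.7% / 5.2% | 63% | 4.3% / 4.8% |

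A separate run at n = 42 gave 8.5%, 12.7% and 20.2% for the rule at skewness 1.0, 1.4 and 2.0, against 5.8%, 6.2% and 6.9% for the t-test.

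**Step 4: direction.** With right skew the excess rejections nearly all say that albumin fell. The rate of false claims of benefit (nominal 2.5%) drops to 1.1%, 0.4% and 0.1% at skewness 1.0, 1.4 and 2.0. With left skew the picture is mirrored, and the excess becomes false benefit.

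**Step 5: levels or changes.** Section 3.1 admits only albumin below 38 g/L, which cuts off baseline levels at the top. Assuming a population mean of 36-38 g/L, SD 4-5 and within-person correlation 0.3-0.7, the check applied to baseline levels switches in 67-94% of trials of 42-50 patients. Applied to changes, it switches in about 5%. In those settings the changes are nearly symmetric (skewness 0.02-0.07), so the unstated choice decides which test is reported without inflating error.

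**Step 6: imputation.** Settings: 4,000 trials of 50, 15% of month-6 values missing completely at random, 20 imputations, normal data. Pooling standardised signed-rank statistics gave a type I error of 4.9%, against 4.6% for the pooled mean change. Power at a 1.5 g/L change was 66.0% against 66.9%.

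**The case against.** Both branches are stated in advance, and section 7.3 likewise pairs non-normal data with median and IQR. Section 7.4 speaks of comparing levels and does not restrict the hypothesis to the mean. If neither the solution nor time has any effect and before and after values are exchangeable, the changes are symmetric and the signed-rank test is valid. The rejections in Step 3 are therefore errors only for the null of zero mean change. At the design effect the choice hardly matters: with a true 3 g/L change and skewness 1 or 2 in either direction, the rule rejects in at least 99% of trials and the t-test in 98-100%. The normality check may also be named in an SAP that is not shown.

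Most of this stands and limits the size of the point. It does not remove it. Section 7.5 makes the mean change the quantity of interest, and naming the normality check would still leave two different hypotheses behind one primary p-value.

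A reader might infer two stronger things. The first is that the Wilcoxon branch cannot be combined with multiple imputation, so that sections 7.4 and 7.6 contradict each other. Step 6 shows otherwise: rank statistics, or a pseudo-median with its standard error, can be pooled. What is true is that Rubin's rules do not apply directly to the signed-rank result. The second is that error is inflated whenever the rule switches. It is not: with symmetric heavy tails the rule switches in more than half of trials and the error stays near 5%.

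**Conclusion.** The point holds in a limited form. Section 7.4 lets the data choose between two tests that have different targets when changes are skewed, while section 7.5 is sized on only one of those targets. For a true zero mean change, the rule's error rate is about 6% at skewness 0.5, 8-9% at 1.0, 12-13% at 1.4 and 20-23% at 2.0, against about 5-7% for the t-test over that range. There is no inflation for symmetric changes. Whether the excess shows as false decline or false benefit depends on the direction of skew.

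These sizes rest on an assumed Shapiro-Wilk check at 0.05 on the changes, and on skewness values that the protocol does not supply. That the two branches test different things does not depend on either assumption. The pooling difficulty is an added inconvenience and not a contradiction.

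**What to change.** In section 7.4, make the mean change in albumin from baseline to month 6 the single primary analysis, by paired t-test with a 95% confidence interval, whatever a normality check shows. State in 7.4 or 7.6 that this estimate is pooled by Rubin's rules where imputation is used. Keep the Wilcoxon signed-rank test as a sensitivity analysis.

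The cost is a few lines of wording, with no change to sample size or visits. With heavy-tailed changes the t-test can be slightly less powerful than the rank test. Here that is negligible: with normal changes, paired-t power for 3 g/L at SD 4 is 99.7% at n = 42 and 99.9% at n = 50.

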7.5 Sample Size Justification

Based on a pre-study pilot ($n=20$), the standard deviation (σ_d) of serum Alb changes is 4 g/L, and the clinically meaningful difference (δ) is 3 g/L. With a two-tailed $\alpha=0.05$ and power=80%, the minimum sample size is 14. Accounting for a 15% withdrawal rate, 50 participants are enrolled to ensure result robustness.

7.6 Missing Data Handling

Missing data will be addressed using multiple imputation methods to minimize bias in the analysis results.

8. Data Management & Quality Control

- **Data Collection:** Use Electronic Case Report Forms (eCRFs) combined with paper records; anonymize data using unique study IDs to protect participant privacy.
- **Data Verification:** Implement double data entry, with all modifications tracked and documented in the audit trail.
- **Equipment Calibration:** Calibrate testing instruments every 3 months to ensure measurement accuracy.
- **Personnel Training:** Provide uniform training on study protocols and Standard Operating Procedures (SOPs) to all study personnel before study initiation.
- **Metadata Removal:** Redact and remove metadata from all electronic documents before submission to ensure compliance with data privacy regulations.

9. Ethics & Compliance

- The study complies with the 2024 Declaration of Helsinki, Good Clinical Practice (GCP), and relevant national regulations.
- Approved by the Ethics Committee of Shanghai Tenth People's Hospital (Approval No.: SHSY-IEC-6.0/26K8/P01; Approval Date: January 9, 2026).
- Informed consent will be obtained from all participants (or legal representatives) before enrollment.
- All personally identifiable information (PII) and confidential commercial information will be redacted before any public disclosure.

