1.3 Exploratory Objective

To explore the mechanism by which Amino Acid (15) Peritoneal Dialysis Solution improves nutritional status in peritoneal dialysis patients through intra-abdominal amino acid supplementation.

2. Study Design

- **Study Type:** Interventional clinical study
- **Design:** Single-center, prospective, open-label, self-controlled (before-and-after comparison)

- **Total Study Duration:** 24 months (from study initiation to final report completion)
- **Intervention Period per Participant:** 6 months (starting on the enrollment day)
- **Sample Size:** 50 participants

3. Study Population

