4.3 Concomitant Medications

- Participants must maintain stable doses of medications affecting protein metabolism and nutritional supplements throughout the study period.
- Any necessary dose adjustments due to severe clinical complications (e.g., severe infection) will result in participant withdrawal, with follow-up until symptoms stabilize.

5. Outcome Measures

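### Multiple imputation has no separate handling of participants who stop the product, and the only named sensitivity analysis (PP) leans the same way, so optimistic imputation would go undetected

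*Protocol*

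**What the plan says.** - **Design (Protocol section 2):** "Single-center, prospective, open-label, self-controlled (before-and-after comparison". There is no control group.
- **Primary outcome (5.1):** serum albumin, "Measured at baseline (enrollment day), 3 months, and 6 months post-intervention".
- **Primary test (7.4):** "Compare serum Alb levels before and after intervention using paired t-tests (if normally distributed", with a Wilcoxon signed-rank test as the alternative.
- **Analysis sets (7.2):** for ITT, "All enrolled participants will be included in the ITT set, regardless of protocol adherence". For PP, "Participants who complete the full intervention and have no major protocol violations will be included in the PP set for sensitivity analysis". No other sensitivity analysis is named.
- **Missing data (7.6):** the whole provision is "Missing data will be addressed using multiple imputation methods to minimize bias in the analysis results". It names no imputation model and no assumption about why values are missing, and it does not distinguish participants who stopped the product.
- **Leaving the study:** under 4.3, a dose change of a restricted medication or supplement forced by a severe complication, such as severe infection, "will result in participant withdrawal, with follow-up until symptoms stabilize". Section 3.3.1 adds missed dialysis, missed visits and less than 3 months of intervention. The withdrawal visit in 6.2 covers safety assessments and an undefined supplementation of data. It does not schedule a month-6 albumin.
- **Exclusion (3.3.2):** participants with more than 10% of required outcome measures missing are excluded.

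**The concern.** An ITT set that ignores adherence asks what happened to albumin in everyone enrolled, including those who stopped. Multiple imputation can answer that only if the imputation model has information on people who stopped. Here it would have very little. There is no control arm, and month-6 values come almost only from participants still receiving the solution. An ordinary missing-at-random model would therefore estimate what stoppers would have gained had they stayed on, which is a different quantity.

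A sensitivity analysis should be able to show this. PP cannot, because it uses the same completers. The two results would agree and could be read as evidence of robustness. What is at stake is the reported size of the albumin gain, which readers will set against the 3 g/L that the protocol itself calls clinically meaningful.

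**Working it through.** **1. The plan's own figure.** Section 7.5 states that the SD "of serum Alb changes is 4 g/L", a difference of 3 g/L, two-sided alpha 0.05 and 80% power.

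n = ((1.960 + 0.842) × 4 / 3)² = 13.95, so 14. This matches the protocol. (An exact t calculation gives 16.) With 15% withdrawal, 14 / 0.85 = 16.5, so 17. The trial enrols 50, of whom 15% is 7.5 participants.

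**2. Size of the overstatement.** Let d be the share who stop, s their true mean change, and 3 g/L the completers' gain. The 15% is the protocol's. Its 3 g/L is a planning difference, used here as an assumed gain. The values of s are assumptions, because the protocol gives none. Month 6 is taken as the time point after intervention.

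- True all-enrolled mean = (1 − d) × 3 + d × s
- Standard imputation and completers-only both estimate about 3
- Excess = 3 − true mean = d × (3 − s)
- SD across all enrolled = √(16 + d(1 − d)(3 − s)²)

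With d = 0.15 and N = 50:

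| Assumed s (g/L) | True mean | Excess | SD | Power at the true mean |
|---|---|---|---|---|
| +1.5 | 0.85×3 + 0.15×1.5 = 2.775 | 0.225 | 4.04 | 99.8% |
| 0 (back to baseline) | 0.85×3 = 2.55 | 0.45 | 4.14 | 99.0% |
| −1.5 | 2.55 − 0.225 = 2.325 | 0.675 | 4.31 | 96.2% |
| −3 | 2.55 − 0.45 = 2.10 | 0.90 | 4.54 | 89.4% |

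In relative terms, a return to baseline gives 0.45 / 2.55 = 18% too high.

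**3. Would PP reveal it?** A simulation used 2,000 trials of N = 50 with 8 stoppers and 20 regression imputations on baseline and month-3 albumin. It assumed a baseline SD of 3 g/L and a correlation of 0.6 between the 3- and 6-month changes.

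| Stoppers' true change | Imputed mean | Completers-only mean | True mean |
|---|---|---|---|
| 0 (early, mixed or late stopping) | 3.00 to 3.01 | 3.00 to 3.01 | 2.52 to 2.53 |
| −3 (mixed) | 2.99 | 2.99 | 2.03 |

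The gap from the truth is built in by the assumed stopper change, so the simulation does not show that bias exists. It shows that the two planned analyses coincide whether or not it does. The rejection rate was 99.7 to 99.8% with imputation against 98.7 to 99.0% on complete data in the first row, and 99.7% against 90.0% in the second.

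**4. Effect of section 3.3.2.** Sections 5.1 and 5.2 list 12 measures at baseline, 12 at month 6, one month-3 albumin and about 13 biweekly ultrafiltration records: 12 + 12 + 1 + 13 = 38. Missing month 6 alone is 12 / 38 = 32%, well above 10%. If the exclusion applies to the analysis, most stoppers are removed rather than imputed. What remains resembles the completers, so the estimate again sits near 3 g/L, and the set no longer contains all enrolled participants.

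**The case against.** **The imputation model is not stated.** A reader might infer from 7.6 that every missing value will be drawn from participants still on the product. The section does not say so. Return-to-baseline or delta-adjusted imputation would also fit its sentence, and a SAP that is not shown may specify the model. This stands, so the point is conditional on standard imputation. It does not rescue PP, which the protocol names as the sensitivity analysis and which uses completers under any imputation model.

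**Some data on stoppers may exist.** The month-3 albumin and the supplementation of data at the withdrawal visit could inform the model. This stands in part. If albumin is already low at month 3 in those who later stop, imputation will carry some of that forward. But the withdrawal content is undefined, those who leave before month 3 have no scheduled post-baseline albumin, and a month-3 value taken on product says little about albumin after stopping.

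**The direction is assumed.** A reader might infer that the ITT estimate will be too high. The protocol gives no stopper outcomes, so this follows only if stoppers do worse than comparable completers. Withdrawal after severe infection makes that plausible but does not establish it. Entry below 38 g/L also allows regression to the mean, so zero change is not a neutral anchor.

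**The consequence is limited.** This stands. Section 7.4 tests before against after, not against 3 g/L, and no stated success rule uses that figure. Section 3.3.3 refers to meaningful differences without giving a number.

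**Death and leaving dialysis.** A reader might also infer that 7.6 requires imputing albumin after death, or dialysis measures after peritoneal dialysis has ended. It does not say that such values count as missing. Handling them is ordinary analysis-plan detail and is not part of this point.

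**Conclusion.** The point holds in conditional form. As planned, multiple imputation has no separate handling of stoppers, and its only named check shares its dependence on completers. If standard missing-at-random imputation is used and stoppers do worse than comparable completers, the all-enrolled gain is overstated by about 0.2 to 0.9 g/L, or 0.45 g/L if stoppers return to baseline. That rests on the protocol's 15% withdrawal, an assumed 3 g/L gain in completers and assumed stopper changes of +1.5 to −3 g/L. The effect is on the size of the gain relative to 3 g/L. Power at the true means stays between 89% and 99.8%, so the significance result would seldom change.

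Separately, and whatever the imputation model, the exclusion in 3.3.2 contradicts the all-enrolled ITT set in 7.2 if it applies to the analysis. It would lean the same way under the same condition. Sections 3.3.2, 7.2 and 7.6 need to be reconciled.

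**What to change.** 1. In 3.3.2 or 7.2, state that having more than 10% of measures missing does not remove a participant from the ITT set.
2. In 7.6, add a sensitivity analysis for participants who stopped the product and have no month-6 albumin. Either impute month 6 around their own baseline, or apply a range of delta adjustments to the standard imputation. Report it beside the standard result.
3. In 7.2, describe PP as supportive only, and do not take its agreement with the imputed ITT result as evidence of robustness to dropout.

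The cost is a few sentences and one extra imputation run, with no additional participants or visits. The sensitivity estimate may be less favourable. Return-to-baseline may also be conservative, because entry at low albumin allows some rise without the product. A range of deltas shows how far the conclusion depends on that choice.
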